### **Procedures of MMTT:**

The MMTT is a standardized method of measuring PPG level. In this study, MMTT is conducted to assess the impact of HMS5552 on PPG, insulin, and C-peptide. (Note: in this study, all meals for MMTT are referred to instant noodles standard meal provided by the Sponsor. The usage method and cautions are described in Appendix 3).

If a subject withdraws from the study early, and already has discontinued study medications at the termination visit, the MMTT is not needed (in other cases, the procedures are consistent with Visit 15).

## **7. Safety Assessments**

### **7.1 Adverse Event (AE)**

AE refers to any untoward medical occurrence, including exacerbation of a pre-existing condition, in a patient or a subject in a clinical study who has been administered with an investigational drug, no matter its causal relationship with the investigational drug. An AE can

therefore be any unfavorable and unintended disease (e.g., acute appendicitis), symptom (e.g., nausea, chest pain), sign (e.g., tachycardia, hepatomegaly), or abnormal laboratory finding (e.g., laboratory tests, ECG).

AEs include serious and non-serious AEs.

### **7.1.1 Serious Adverse Event (SAE)**

SAE is defined as an AE occurring in any period of the study (i.e. run-in, treatment, follow-up) that meets one or more of the following criteria:

1. Resulting in death
2. Immediately life-threatening

The term "life-threatening" refers to an event in which the subject is at immediate risk of direct death at the time of the event. It does not include the situation that might lead to death if it were more severe. For example, drug-induced hepatitis resolved without hepatic failure cannot be considered as life-threatening though it might be fatal.

3. Requiring hospitalization or prolonged hospitalization

Hospitalization or prolonged hospitalization due to elective surgery, routine clinical procedures, social reasons or self-convenience do not need to be recorded as an AE. If the events meet AE criteria e.g., aggravation from previous condition, they should be reported as "serious" or "non-serious" AEs based on routine criteria.

4. Resulting in persistent or significant disability/incapacity
5. Congenital anomaly/birth defect
6. Important medical event: to preclude one of the outcomes listed as above, medical and scientific judgment should be made to assess whether other situations should be considered as serious, such as important medical events that may not be immediately life-threatening or result in death or hospitalization but may jeopardize the subject or may require medical intervention. Examples of such events include allergic bronchospasm requiring intensive treatment in an emergency room or at home; blood dyscrasias or convulsions that do not result in hospitalization; drug dependency or drug abuse, etc.

### **7.1.2 Persistent or Recurrent AEs**

Persistent AEs are events that continuously exist during the assessment period without resolution. These events should be recorded only once on eCRF. The initial severity of this event should be recorded, and the highest severity should be updated once the event is aggravated. If the event becomes an SAE, corresponding update should be made on eCRF to reflect this situation.

Recurrent AEs are events that are recovered during the assessment period, but reoccur afterwards. Each recurrence must be recorded separately on the AE page of eCRF.

### 7.1.3 AEs Related to Examinations and Laboratory Tests

Abnormal results from examinations and laboratory tests (such as hematology, blood biochemistry, urinalysis, ECG, physical examination, vital signs, etc.) at screening are regarded as pre-existing condition before the ICF is signed and do not need to be recorded as an AE. Clinically significant abnormality at screening can be recorded as relevant medical history according to the Investigator's judgement. The Investigator is responsible for assessing all abnormal results of examinations and laboratory tests for clinical significance. Any abnormality meeting the following criteria is considered as clinically significant and should be reported as an AE:

- The abnormality that suggests a disease and/or organ toxicity that is new or has worsened from baseline.
- The abnormality that needs the investigational product dosage and usage to be adjusted, e.g., dose change, drug discontinuation, etc.
- The abnormality that requires additional active intervention, e.g., increase or modification of the concomitant medications, close observation, more frequent follow-up assessments, or further diagnostic examination, etc.

If the laboratory abnormality of clinical significance is a manifestation of disease (e.g. alkaline phosphatase and total bilirubin increase with cholecystitis), then only the diagnosis (i.e., cholecystitis) will be recorded as an AE. If laboratory abnormality of clinical significance is not a manifestation of disease, then the abnormality will be recorded as an AE. Appropriate description will be used to record if the test results are lower or higher than normal range (e.g. "serum potassium increase" rather than "abnormal serum potassium"). If the result meets diagnostic criteria, the clinical diagnosis will be recorded as an AE. For instance, when serum potassium increases to 7.0 mmol/L, it can be recorded as "hyperpotassemia".

## 7.2 Recording of AEs

### 7.2.1 Terms of AEs

All AEs reported by subjects or found by the Investigator are recorded and described on eCRF in accurate and standard medical terminology. The diagnosis is recommended to be used as the term for the AE. If no diagnosis, the symptoms, signs, or laboratory abnormality can be reported as the term of the AE. When a diagnosis is determined afterwards, the record can be updated accordingly.

### 7.2.2 Recording of AE Time and Collection Period for AE

The Investigator should try to collect the start and end dates of each AE. Correct records of AE

start time are helpful in assessing the temporal relationship between AE and drug administration. Usually, the AE start date should be the date of symptom onset. If the AE aggravates from the baseline medical conditions, the AE start date is the date of condition aggravated. If the AE is newly happened in the study and progressed to SAE, the SAE start date should still be the AE start date.

In this study, AEs (except for SAEs) are collected from the first dose of study medication in run-in period to the last visit.

The SAEs are collected from the first informed consent form is signed to the last visit.

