## 8.6 Database Lock

Two stages are planned for database lock in this study.

The first database lock is scheduled at the completion of the double-blind treatment for all subjects. After the blinded data review meeting, the principle investigator, sponsor, and biostatistician must sign off all related documents before the database lock (DBL). DBL is limited to the double-blind treatment data, but not the data in the open-label treatment period. No update is permitted to locked data in principle. Errors found after DBL should be evaluated to determine whether database unlock is necessary for data correction. Documentation must be recorded if database unlock is required.

The second database lock is scheduled at the completion of the open-label treatment. A regular data review meeting is required before the final DBL. The investigator, sponsor, and biostatistician should sign off relevant documents before DBL. In principle, no update is permitted to locked data. Errors found after database lock should be evaluated to determine whether database unlock is necessary for data correction. Documentation must be recorded if database unlock is required.

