#### 6.1.1. Imputation on Start / End Date of Adverse Events

Partial start/end dates for any adverse events will be imputed using the following convention.

For start date of adverse events,

1. Day Missing— impute with the first day of the month. If both month and year

are the same as those of the first dose administration in double-blind treatment period, then impute with the first dose administration date in double-blind treatment period.

2. Day and Month Missing – impute with January 1st. If year is the same as that of the first dosing in double-blind treatment period, then impute with the first dosing date in double-blind treatment period.
3. Completely Missing - impute with the first dose administration date in double-blind treatment period. If end time of adverse event is earlier than the date of the first dose administration in double-blind treatment period, then impute with the date of informed consent form.

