### 9.3.2. Adverse Events

Adverse events will be coded using MedDRA version 22.0.

Adverse events start before the first exposure to study treatment in double-blind treatment period will be included in the listing of all adverse events.

Treatment emergent adverse events (TEAEs) will be summarized for double-blind period and open-label period respectively. TEAEs are defined as any adverse event present after the first exposure to study treatment or any already presented events that worsened after the first exposure to study treatment.

TEAEs in double-blind treatment period: any adverse event present after the first exposure to study treatment or any already presented events before first double-blind dose administration that worsened after the first exposure to study treatment till the end of double-blind treatment period.

Treatment related adverse events: Adverse events that “Related” or “Probably related” to study treatments.

Important Adverse events: any adverse events, except serious adverse events, leads to results in actions of medical treatment (such as dose discontinuation, dose reducing or symptomatic approach treatment) and abnormal hematological or other lab test results.

Incidence rate of adverse events, treatment related adverse events, serious adverse events and adverse events result in withdrawal from study will be summarized and counted by SOC/PT for each treatment group. The frequency of AEs will be counted for each subject only once per PT name. The difference incidence rate between treatment groups will be compared using Fisher’s Exact test.

Adverse Events will be summarized by severities, if an adverse event occurs more than once on a given subject, then the worst will be counted.

Adverse events with incidence rate  $\geq 2\%$  and  $\geq 5\%$  will be summarized by PT name.

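### AEs that begin in run-in or on placebo and later worsen have no listed date of worsening, and the SAP has no open-label anchor, so some cannot be assigned to the right treatment period

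*Supplement*

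**What the plan says.** **Recording (protocol v1.1).** Collection of non-serious AEs starts with the first run-in placebo dose (7.2.2). On persistent AEs, 7.1.2 says: "These events should be recorded only once on eCRF". On severity: "The initial severity of this event should be recorded, and the highest severity should be updated once the event is aggravated". On seriousness: "If the event becomes an SAE, corresponding update should be made on eCRF to reflect this situation". Section 7.2.2 dates an event that is new in the study and has "progressed to SAE, the SAE start date should still be the AE start date". A pre-existing condition is treated differently: "If the AE aggravates from the baseline medical conditions, the AE start date is the date of condition aggravated". Each recurrence of a resolved AE gets its own record (7.1.2). The variable list in 7.2.3 has start and end dates and, where applicable, hospitalization, discharge and death dates. It has no date of severity change and no date of becoming serious.

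**Analysis (SAP).** Section 9.3.2 summarizes treatment-emergent events (TEAEs) for the double-blind and the open-label period. For the double-blind period the definition includes "any already presented events before first double-blind dose administration that worsened after the first exposure to study treatment". The open-label period has no definition of its own. Under 6.1.1, a start date with unknown day is handled thus: "impute with the first day of the month", unless that month and year are those of the first double-blind dose, in which case that dose date is used. No rule refers to the first open-label dose.

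**Design.** Placebo subjects who continue switch to HMS5552 after Week 24 (protocol 5.1.3).

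**The concern.** The TEAE rule turns on when an event worsened, but the recording rules keep only that it worsened. An AE that begins before HMS5552 is taken and becomes severe or serious while it is taken stays under a start date from before exposure.

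Safety of HMS5552 through the open-label phase is a stated aim of the trial, and it rests on assigning events to the right period. Protocol 1.3 reports no SAEs in the completed studies (1.5 says only no related SAEs in phase II), so single serious events would be read closely.

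**Working it through.** The plan gives no figure to reproduce, and the point rests on rules rather than on a calculation. I set the recording rules against the SAP rule for each type of event.

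1. **Pre-existing condition that worsens on treatment.** The AE start date is the date of aggravation (7.2.2). The TEAE rule works.
2. **AE that resolves and recurs on treatment.** New record, new start date (7.1.2). The rule works.
3. **AE that starts in run-in, never resolves and worsens.** Section 7.1.1 counts run-in as a period of the study, so the natural reading is that this event is new in the study. It stays one record under its original date. Initial and highest severity show that it worsened, but nothing listed shows whether this was before or after the first double-blind dose. Only a hospitalization or death date would tell. The worsening limb is otherwise undetermined, in either arm.
4. **AE that starts on double-blind placebo, never resolves and worsens on open-label HMS5552.** The start date is in the placebo period. The SAP has no open-label definition, and first exposure is not reset at the switch. By start date the event falls under placebo.
5. **AE that starts on HMS5552.** Drug attribution is unaffected.

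**Partial start dates in placebo-switch subjects (SAP 6.1.1).** The switch comes about 168 days after the first double-blind dose (Visit 10, Day 168 ± 4), so the two never share a calendar month.
- *Day unknown, month of the switch:* imputed to the 1st. If the switch is on day d > 1, this precedes the switch. An AE that truly began between day d and the end of the month is assigned to placebo.
- *Day and month unknown, year of the switch:* imputed to the first double-blind dose if that was in the same year, otherwise to 1 January. Both precede the switch (unless it fell on 1 January), so the result is placebo.
- *Wholly unknown:* imputed to the first double-blind dose, or to the consent date if the AE ended before that dose. Never open-label.

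**Scale.** Placebo arm: 450/3 = 150 planned, 564/3 = 188 at the cap. One subject is 1/150 = 0.67% or 1/188 = 0.53%. This is the weight of one event, not an estimate of how many there are, and fewer subjects than this will reach the switch.

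**The case against.** The case on the other side is substantial and limits the point.

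- **A reader might infer that the worsening rule cannot be applied at all.** The documents do not support that. Pre-existing conditions and recurrences are dated correctly, initial severity is kept beside the highest, and hospitalization or death dates can time some SAEs. An event that starts on placebo and leads to hospitalization in the open-label period could be timed this way, although no SAP rule says to do so.
- **A reader might infer that the whole error favours HMS5552.** That holds only for the switch and the partial dates. The run-in gap applies equally to both randomized arms.
- **A reader might infer that such events vanish from the safety report.** They do not. SAP 9.3.2 puts earlier-starting events in the listing of all AEs without saying they go only there. SAP 5.4 has a display from baseline to Week 52 with a placebo-then-HMS5552 group, where a switch event still counts. Only its period is in doubt.
- **The first limb of the TEAE definition** covers events present, not only events starting, after first exposure. Read literally, it would capture an ongoing run-in event. It would also make the worsening limb redundant, so the wording needs settling either way.
- **A reader might see a contradiction with the first database lock.** Section 8.6 says "No update is permitted to locked data in principle", while 7.1.2 requires a record to be updated when it worsens. The words leave room, and an unlock path exists. That path is for errors, however, and later worsening is not an error. The update route is unstated rather than barred.
- **The eCRF is not shown.** It, or the SAE report form, may hold the missing dates.

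**Conclusion.** The point holds for a limited set of events: AEs that begin in run-in or on double-blind placebo, stay unresolved and later worsen, and AEs in placebo-switch subjects with a partial start date that could fall on either side of the switch. For the first set, the timing the SAP needs is not among the listed variables unless a hospitalization or death date supplies it. For the second, the imputation rule places the event on placebo regardless of when it began, except in the edge case of a switch on the 1st of the month (or on 1 January when only the year is known).

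The switch and partial-date problems move events from HMS5552 to placebo. The run-in gap has no established direction. The documents give no AE rate, so the size is unknown. The conclusion assumes that the eCRF collects what 7.2.3 lists and no more, and that TEAE status is decided from start and end dates, as SAP 6.1.1 implies. It is worth correcting because stated rules would put some events in the wrong period and the repair is small. The primary efficacy analysis is not touched.

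**What to change.** 1. **Protocol 7.1.2, 7.2.2 and 7.2.3, and the eCRF.** For AEs ongoing at the first double-blind or first open-label dose, record the date of worsening and the date the event became serious, or open a linked record at worsening. State how a record locked at the first database lock is updated.
2. **SAP 9.3.2.** Add an open-label TEAE definition anchored to the first open-label dose. Assign worsened events by the date of worsening. Treat a run-in AE that worsened at an unknown time as treatment-emergent. Say whether the first limb means events that start, or events that are present, after first exposure.
3. **SAP 6.1.1.** In the open-label analysis of placebo-switch subjects, impute a partial start date compatible with the month (or year) of the first open-label dose to that dose date, unless the AE ended earlier.

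**Cost.** Two date fields or a few linked records, and some SAP text. Incidence counted once per subject per preferred term within a period is not inflated. The conservative rules in items 2 and 3 will count some events as emergent on treatment, or on HMS5552, that were not; the report should say so. If data are already collected, items 2 and 3 can still be made before unblinding, with hospitalization and death dates used where they exist.

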### **7.2.3 AE Variables**

The following variables are collected for each AE:

- Term (verbatim)
- Start and end dates/time
- Severity
- Serious adverse event or not
- The SAE criteria
- Action taken for study medication
- Outcome
- Assessment made by the Investigator on the causal relationship to study medication
- Assessment on the causal relationship to study procedures
- Assessment on the causal relationship to other medications, hospitalization date (if applicable)
- Discharge date (if applicable)
- Possible cause of death (if applicable)
- Date of death (if applicable)
- Autopsy (if applicable).

### **7.2.4 AE Grading**

AEs are graded by severity as mild, moderate and severe:

**Mild:** appearance of signs or symptoms, but can be easily tolerated.

**Moderate:** obvious discomfort interfering normal daily activities.

**Severe:** incapacitating, and can't perform normal daily activities.

### 7.2.5 AE Outcome

The outcomes are described as follows:

- Recovered/resolved: the subject returns to baseline state.
- Recovering/resolving: the event hasn't been resolved completely, but the subject is improving.
- Not recovered/not resolved: the event is ongoing, e.g., irreversible congenital anomaly.
- Recovered/resolved with sequelae: only if the subject suffers from lifetime sequelae, e.g., blindness caused by diabetes, and the hemiplegia after a stroke.
- Fatal: the death date is the date for event ending.
- Unknown: the Investigator can't obtain the outcomes of the AE, e.g. the subject is lost to follow-up.

If an AE is assessed as "recovered/resolved", "recovered/resolved with sequelae", or "fatal", the AE ending date must be recorded.

The Investigator must follow up all AEs. When the study is completed, any AEs that are unresolved or don't have outcomes should be followed up by the Investigator until the events are resolved or considered stable, which don't have to be recorded further on eCRF (e.g. after database lock). The follow-up information on SAEs that occurs after database lock needs to be reported to Clinical Drug Safety department of the Sponsor. The contact information is:

Email: [[contact]](mailto:[contact]), Fax: [name], [contact].

### 7.2.5 Causality Assessment

The Investigator should assess the causal relationship between the AE and the study medications through medical and scientific judgement. The following criteria can be referred to:

1. **Related:** The AE occurrence follows a reasonable temporal relationship with administration of the study medication. The AE is consistent with the known profile of the study medication. The event is improved when the dose of study medication is decreased or stopped. The event reoccurs when the study treatment is restarted. The AE can't be explained by subjects' medical condition or alternative treatment.
2. **Possibly related:** The AE occurrence follows a reasonable temporal relationship with

administration of the study medication. The AE is consistent with the known profile of the study medication. The AE alleviates or becomes not obvious after reducing the dosage or stopping the study medication. The subjects' medical condition or alternative treatment may lead to the event.

3. **Unlikely related:** The temporal relationship between the AE occurrence and administration of the study medication is not clear. The AE may not be consistent with the known profile of the study medication. The subjects' medical condition or alternative treatments may lead to the event.
4. **Not related:** There is no reasonable temporal relationship between the AE occurrence and administration of the study medication. The AE is not consistent with the known profile of the study medication. The subjects' medical condition or alternative treatments may lead to the event. The AE improves or disappears when the disease condition improves or alternative treatment is stopped.

### 7.3 SAE Reporting

Once an SAE occurs in the study, the Investigator must immediately take appropriate measures for treatment and report the SAE to the relevant drug administration departments, health administration departments, ethic committees and the Sponsor within 24 hours after awareness. The Investigator needs to ensure the SAE information be recorded on eCRF timely.

When completing the SAE report form (CFDA version), the Investigator must also collect the SAE information requested by the Sponsor. Refer to the Investigator Site File for the details of SAE reporting.

### 7.4 Hypoglycemia

The Investigator must correctly instruct subjects to conduct the SMBG (refer to Appendix 4 procedures for SMBG) to identify and manage hypoglycemia. Subjects should measure their fasting and postprandial fingertip blood glucose at least twice a week, and record in subject diaries. Any symptoms of hypoglycemia should be recorded in subject diaries. The subjects should be instructed to measure blood glucose when hypoglycemia symptoms appear, and also to carry carbohydrates that can be easily taken for hypoglycemia management.

Hypoglycemia event should be recorded on the hypoglycemia evaluation page of eCRF. Detailed information listed below must be recorded for each hypoglycemia occurrence: start date and time, end date and time, blood glucose values, symptom description, action taken, severe hypoglycemia or not, resolved or not, precipitating factors, causal relationship with the study medication, etc.

Refer to Section 4.5.1.1 of the protocol for the hypoglycemia assessment and classification criteria.

